SRPSAT38 I am satisfied with the amount of time I spend performing my daily routines					

Báa nnilah program qualitative interview questions

Hello. I am [name]. Thank you for agreeing to talk about your experiences with the Báa nnilah program. We plan to use the information shared in the interviews to improve the program for the future. We hope you will share with us your true feelings, for there are no right or wrong answers to these questions. We will be tape-recording our conversation so that we make sure to receive everything that you have to share. Participation in this interview is voluntary and you can choose to either share your name or have the information you share be anonymous, meaning that your name will not appear anywhere. You can stop the interview at anytime or not answer any question. The interview will take about one hour of your time and you will be paid a \$30 gift card to thank you for your help. Let's begin.

- How did participating in the Báa nnilah program impact your life?
- How did your Báa nnilah program mentor impact your life?
 - What information did you learn from your mentor?
 - How did the mentor's teaching style impact your learning?
- What have you shared about the program with community members and others?
 - How have you shared about this program?

(Give participant the list of gathering topics for the next set of questions.)

[figure not shown]
- What have you changed about your self-care after participating in the Báa nnilah program?
 - What information/tips/techniques from the Báa nnilah program did you apply or are you applying to your own life?
- If you think about how you talked with others about your health before and after being in Báa nnilah – how has it changed?
- What has changed in your relationships with your family and friends since being in Báa nnilah?
- What has changed in your relationship with your doctor since being in Báa nnilah?
 - How has the communication between you and your doctor changed?
 - How has your doctor's attitude changed since being in Báa nnilah?
 - Ask about concern and thoroughness if they don't mention these
 - How has the doctor's behavior and treatment toward you changed?
- Which parts of the program (which gathering) were most helpful?
- Which parts of the program (which gathering) was least helpful?
- What would you change to make the program better for the future?
- Since starting with the Báa nnilah program, what other support in addition to being in the program has made a difference for your health?
- In your observation, what changes have you noticed in the community as a result of this program?
- What do you see for yourself for the future?
 - What information/tips/techniques from the program will you use in the future?

- What ideas do you have for the future of the Ba nnilah program in the Crow community?

Aho. Thank you for your time today. You are helping us to make the Ba nnilah program most effective.

Facilitator measures of fidelity

1. Recruitment: Mentor will have a “Participant Notebook” where they keep track of names and contact information of community members they recruited, location of recruitment, and date of recruitment. We will also gather information on emergency contacts for each participant. We will use this notebook to track recruitment efforts. Note: The Participant Notebook will not be linked to the outcome data in order to protect confidentiality of participant information.
2. Entry into study: The Participant Notebook will also have information on the date the mentor consented the participant and the date they held a meeting with the participant to hear their health story.
3. Retention:
 - a. Each gathering will include a mentor check list of participant attendance, which the mentor will transfer into the Participant Notebook, which will be changed to number of gatherings attended by each participant in the database.
 - b. For gatherings missed by participants, the mentor will indicate if the participant provided a reason for missing the gathering
 - c. Participants who drop out of the study will be contacted by project staff (not the mentor who is leading their gatherings) and asked for their reasons for drop out.
4. Dose: Each gathering will include a mentor check list of which components of the gathering they facilitated and the length of the gathering in minutes. An example is included in the materials. The evaluation will consist of the number of manual-based intervention components delivered divided by the total number intended. The checklist also includes three questions:
 - a. How comfortable were you in leading this gathering?
Not at all comfortable to Very comfortable on a scale of 1-10
 - b. How confident were you in leading this gathering?
Not at all confident to Very confident on a scale of 1-10
 - c. Please share any comments you have about leading this gathering.

Mentor Gathering Check List

Please complete this check list after the gathering has taken place. Please check the box to the right to show which activities you were able to complete during the gathering and answer the questions below. Return the completed check list to [name] or [name]. Thank you!

Mentor name: _____

Date of gathering: _____

Length of gathering: _____ minutes

Gathering 1: Beginning the Bábí nnilah Journey Outline

[figure not shown]
Welcoming, prayer, meal	
Story	
Mentor provides information: introduction/purpose of gathering	
Supportive partnerships activity	
Closing	
How comfortable were you in leading this gathering? Circle one number: Not at all comfortable 1 2 3 4 5 6 7 8 9 10 Very comfortable	
How confident were you in leading this gathering? Circle one number: Not at all confident 1 2 3 4 5 6 7 8 9 10 Very confident	
Please share any comments you have about leading this gathering.	

Join us!

[name], [name] and mentors who have ongoing health concerns (see back) will lead the Baa nnilah program. Messengers for Health is collaborating with all tribal entities, MSU - Bozeman and Big Horn Valley Health Center in Hardin.

Baa nnilah Program Gatherings will begin in 2017

Messengers for Health is expanding our programming to serve both men and women living with chronic illness and recurring health concerns including but not limited to arthritis, cancer, diabetes and heart disease.

Our Baa nnilah program was inspired from personal stories that community members shared with [name] about what helps and what makes it harder for them to manage their ongoing health concerns.

Crow community members who have been living with chronic health concerns and are doing well with their self-care, known as mentors, will in turn encourage others who are facing similar medical challenges. Baa nnilah mentors provide real-life experience, knowledge and cultural strength for our Crow brothers and sisters with on-going health concerns that may not be available in most medical services.

Messengers for Health will work to keep the program going long-term to help inspire a healthier Crow People.

Baa nnilah Program at a Glance

This program is free for any Crow men and women who are living with on-going health concerns and consists of a total of 7 gatherings. Participants will attend all 7 gatherings which include a free meal. Family members are welcomed to be involved and attend the gatherings.

- Gain knowledge and tools for healthy living and self-care to improve your quality of life.
- Learn from mentors and other program members
- Share and apply Crow cultural strengths to address ongoing health concerns.
- Learn about nutrition and physical and emotional health tools and exercises through hands-on activities.
- Gain support and help from program staff and other participants to apply what is learned to your self-care.

Messengers for Health will also host Baa nnilah community meetings to receive input and share our progress so we can better serve our Crow People.

Together let's take back our health!

Journey through the *Báa nnilah* Program

Our 10 mentors will each recruit 20 participants. Eligible participants have an ongoing illness and are 25 and older. Participants sign forms & identify family members and friends who want to be in a group together. By August 15, 2017.

Family members and friends who want to be together are randomly assigned to Fall (Nov 2017-Feb 2018) or Spring (April-July 2018) groups. There will be about 10 participants per group and 10 groups each in Fall and Spring.

Fall and Spring group participants come to orientation and fill out health surveys in local communities.
October 2017

10 Fall groups attend 7 *Báa nnilah* gatherings in local communities

Nov 2017-
Feb 2018

10 Spring groups stay in contact

Fall and Spring group participants fill out health surveys in local communities. March 2018

10 Fall groups stay in contact

April-July
2018

10 Spring groups attend 7 *Báa nnilah* gatherings in local communities

Fall and Spring group participants fill out health surveys in local communities. August 2018

Fall and Spring group participants fill out health surveys in local communities. December 2018

Báa nnilah information

- This program is for Crow men and women who have an ongoing illness.
- It is a partnership with MSU-Bozeman.
- There will be 7 gatherings in local communities - everyone will attend all 7 gatherings.
- Local mentors will lead the program.
- You will gain knowledge and tools for improving your health.
- You will learn from other members and use cultural strengths to address ongoing health concerns.
- There will be hands-on activities to learn about and apply physical activity, nutrition, and emotional health information.
- Members will support and help each other to apply what is learned to your every day life.
- Family members are welcomed to be involved.
- Meals will be served.

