Aim 2: Test the effects of the *Baa nnilah* intervention versus usual care using a wait-list control group effectiveness trial among 200 randomly assigned AI men and women 25 and older who have CI on the Apsáalooke Reservation.

Primary hypothesis: Those AI adults on the Apsáalooke Reservation participating in the *Baa nnilah* intervention will have significant improvement in quality of life using the SF-12 measure compared to a wait-listed control group immediately following the intervention and at 6 and 12 months post-intervention.

[figure not shown]
Secondary hypothesis: Those AI adults on the Apsáalooke Reservation participating in the *Baa nnilah* intervention will have significant improvement in measures of satisfaction in and participation with social roles and activities, social isolation, patient activation, health care relationship, physical function, and depression compared to a wait-listed control group immediately following the intervention and at 6 and 12-months post-intervention. Our mixed-methods design includes a qualitative evaluation of fidelity and acceptability immediately post-intervention.

This study is considered a Phase 3 clinical trial. Please see the attached document, "Protection of Human Subjects" from our grant application that contains human subjects information (some overlap with what is below) and our Data Safety and Monitoring Plan, which is required for Phase 3 clinical trials. This clinical trial has been registered at Clinicaltrials.gov with the following NCT identifier: NCT03036189.

As this project takes place on a reservation, please see the attached letter of support/approval from the Crow Nation.

See picture below for a graphic depiction of our study design:

Research Design of the *Báa nnííłah* Program A Group Randomized Trial

B. RESEARCH PROCEDURES INVOLVED. Provide a short description of sequence and methods of procedures that will be performed with human subjects. Include details of painful or uncomfortable procedures, frequency of procedures, time involved, names of psychological tests, questionnaires, restrictions on usual life patterns, and follow up procedures

There are three different groups from whom data will be gathered. Answers to the questions below are grouped according to who is providing the information.

1. Participants of intervention: all participants
2. Participants of intervention: subgroup
3. Intervention facilitators

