1. Participants of intervention: all participants: 200 Crow community members will be recruited by other community members (described below under D5), provide informed consent (form attached), and be randomly assigned by family/friend cluster to an intervention or wait-list control group (both groups will receive the intervention). Random assignment will occur via cluster so that family members or friends who are interested in participating in the intervention together will remain in the same group. During the month of October 2017, groups of approximately 10 community members will attend an orientation and data collection session – this is the baseline data collection. The groups are based on the community in which they will attend the intervention meetings and include: Wyola, Lodge Grass, Crow Agency, Hardin, and Pryor, MT.

[figure not shown]
During the orientation/data collection session, participants will complete a survey and 3 exercises. All measures in the survey that are in an index form (one measure with multiple questions) come from the NIH PROMIS measure bank (<http://www.healthmeasures.net/index.php>), are other validated measures, or are demographic or fidelity measures used in other studies. All measures

are included with the application and begin with the page labeled "Measures". The survey responses and results of the exercises will be on a tablet computer and will look similar on the computers (the measures attached are in different formats at present).

[figure not shown]
The survey questions will be read out loud by a project staff member. Participants will be seated so that they do not see the responses being entered into other computer tablets by other participants. We are working with the MSU HELPS lab to facilitate data collection. Survey respondents will provide their responses on tablet computers using Qualtrics offline software and unique identification codes. Once a respondent has submitted the survey, those answers will not be viewable by subsequent research participants. The responses will upload to the secure Qualtrics servers once the tablets are again connected to a wi-fi network. Data will not be maintained on the tablet computers in the long term.

Three basic physical function tests will be performed: timed up and go (TUG), static balance assessment (BESS), and 6 minute walk. Brief descriptions of the tests are below. Responses will be entered into the computer tablets.

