Depending on the space available, this can be around the outside of a large room or could be back and forth in a hallway. A step counter is used to record the number of steps the individual takes in the six minutes. Distance walked can then be calculated based on the length of an individual step.

See the research design graphic above: Next, participants in the intervention group will attend the intervention.

The intervention consists of 7 group education sessions (called gatherings), conducted every other week in the local communities and led by community mentors. A manual for the mentors for the education sessions is being finalized at this time so that the sessions remain consistent across mentors and across the intervention and wait-list control groups; all mentors have been recruited and are meeting monthly with project staff to co-develop the intervention materials and receive training. Next, all 200 participants will attend another data collection session in their same groups in March 2018. Next, the waitlist control group will attend the 7 intervention sessions, which will be identical to the intervention group via the mentor manual. All 200 participants will provide outcome measures again in August 2018 and December 2018. The measures will be the same for each data gathering session with the exception of a few questions that will be asked after the intervention only (as noted in the attached measures handout) and are focused on measuring outcomes related to intervention content.

2. Participants of intervention: subgroup. A random sample of 20 participants will be selected – 10 from the intervention group and 10 from the wait-list control group. These participants will be invited to participate in a qualitative interview. [name], Co-PI of this grant will conduct the interviews, which are expected to last approximately one hour. The interview will be audio-taped and transcribed verbatim. Qualitative data analysis methods used in our prior studies will be conducted on this data. Participants will select a location to be interviewed where they are comfortable and where confidentiality will be assured. The questions for the qualitative interview are included with this application and are titled: “Báa nnilah program qualitative interview questions”

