Q10. Please select the type of health insurance or health coverage that pays for your health care. Select all that apply:

- 1. Medicare/Medicaid
- 2. Private insurance
- 3. IHS only
- 4. Other _____

Q11. Does anyone in your household receive benefits from a food assistance program such as WIC, Commodities, SNAP, EFNEP?

- 1. Yes
- 2. No

Q12. Please select the ongoing illness(es) that a doctor has told you that you have. Please select all that apply.

- 1. Diabetes
- 2. Arthritis
- 3. Heart disease
- 4. High blood pressure
- 5. Asthma
- 6. Cancer
- 7. Chronic pain
- 8. Other (they can type in others)

Q13. What is your gender?

1. Female
2. Male
3. Other

This question is for the wait-list control group to be included with the March 2018 data gathering
Q. The Messengers for Health Báa nnilah program consists of 7 gatherings in the local Crow communities and Hardin that are led by a community member mentor. Have you taken action for your health based on something you have learned from a friend or family member who has attended the gatherings?

1. Yes
2. No

These questions are for after participants have completed the intervention:

Rate the following statements				
	very much	somewhat	a little	not at all
I felt like my mentor cared about or was concerned about me.	very much	somewhat	a little	not at all
I felt like the other participants in my B��nnilah group cared about or were concerned about me.	very much	somewhat	a little	not at all
I felt safe and comfortable to openly express my feelings in my group.	very much	somewhat	a little	not at all
I trusted that what I shared in my group would be kept confidential and not shared with others.	very much	somewhat	a little	not at all
After participating in the B��nnilah program, I feel more hopeful.	very much	somewhat	a little	not at all
I would recommend the B��nnilah program to friends or family members	definitely would	probably would	probably would not	definitely would not
The B��nnilah program was helpful to me	Very helpful	Somewhat helpful	A little helpful	Not at all helpful
Gathering 1, with the purpose of sharing how the program grew from the desires and interests of the Crow community to provide support to community members with ongoing illnesses, to become familiar with the	Very helpful	Somewhat helpful	A little helpful	Not at all helpful

program, and to foster and encourage an atmosphere of safety and hope was helpful to me.				

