We would like to make amendments to our IRB application that was approved last fall. In the application, we have three different groups of people from whom data will be gathered.

1. Participants of intervention: all participants
2. Participants of intervention: subgroup
3. Intervention facilitators

1. Participants of intervention: all participants. There are two changes – one to the timeline and one to add a data collection element.

For this group, the actual timeline for group data collection is different from what was proposed in the application. The application has data gathering events occurring in March 2018, August 2018, and December 2018 for the intervention participants. The actual months will be April/May 2018, October/November 2018, and April 2019.

We are proposing to add a data collection element for the intervention participants. All participants attend 7 gatherings as a part of the intervention. The intervention is led by facilitators who are members of the Crow community. Project staff members will send postcard reminders the week before each gathering and text or phone call reminders to participants on the day of each of the 7 gatherings. Project staff will save participant phone numbers only by participant ID number versus by name. Any responses to the text or phone reminders will be archived, again only by participant ID. Additionally, we would like to add questions to the post-intervention survey to ascertain how well each of the retention strategies helped participants to keep attending each of the gatherings (to improve and track participant retention). The questions are below and will be answered on computer tablets with the already approved surveys.

Please check how much each of the following helped you to keep coming to the gatherings

	Not at All	A Little Bit	Somewhat	Quite a Bit	Very Much
Newsletter					
Gifts received at gatherings					
Gas cards received at gatherings					
My supportive partner					
Information I learned at the gatherings					
My personal motivation					
Collecting my feathers (goals)					
Healthy meals at gatherings					
My relationship with my mentor					
My bonding with other participants					
Location of gatherings					
Postcard reminders					
Phone texts/calls from MSU team members					
Phone texts/calls from my mentor					
Other (please explain):					

Please check how much each of the following prevented you from attending the gatherings

	Not at All	A Little Bit	Somewhat	Quite a Bit	Very Much

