Contact information (phone/e-mail): [name]/[contact]
- 4. Requesting modification/amendment to:**

Research protocol
Consent form
Recruitment materials
 Survey instrument, interview questions
Research personnel
Other, please explain:

- 5. Describe the modification being requested:**
Note: with each requested change, provide a detailed description of where within the study documents (e.g. Research protocol, survey instrument, etc.) **the changes are reflected** (e.g., section, question #, etc.)

We would like to make amendments to our IRB application that was approved August 2017. In the application, we had three different groups of people from whom data was to be gathered.

1. Participants of intervention: all participants
2. Participants of intervention: subgroup
3. Intervention facilitators

We would like to make amendments to #1 and to introduce a new group:

4. Participants of modified intervention

1. Participants of intervention: all participants. We have completed data collection 3 times for this group, which consists of our intervention group and our wait-list control group completing the survey approved by the IRB. We would like approval to:

- Make slight modifications to some of the demographic questions to ask if the response changed since the last survey and if it did not, to skip the question. This will hopefully make the survey quicker for participants to complete.
- Remove 2 questions that should not vary over time: 1) gender and 2) year of birth.
- Add a checklist of questions to assess changes in participants since they began the program.

The original questions and changes and the checklist of questions are below.

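### Only the first post-intervention wave has an untreated randomised control, yet comparisons are promised at 6 and 12 months and the SAP names no contrast at that wave

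*Protocol*

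**What the plan says.** Protocol VII.A, Aim 2, describes a test of the "intervention versus usual care using a wait-list control group effectiveness trial". The primary hypothesis promises improvement "compared to a wait-listed control group immediately following the intervention and at 6 and 12 months post-intervention", and the secondary hypothesis uses the same three time points.

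The procedures describe a crossover. Protocol VII.B.1 says "both groups will receive the intervention" and, after the March 2018 assessment, "Next, the waitlist control group will attend the 7 intervention sessions, which will be identical to the intervention group via the mentor manual". The participant handout dates the two deliveries November 2017 to February 2018 for the Fall groups, "or Spring (April-July 2018) groups". The Measures section plans a contamination item: "This question is for the wait-list control group to be included with the March 2018 data gathering".

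A later IRB amendment moves the assessments: "The actual months will be April/May 2018, October/November 2018, and April 2019". It gives no new gathering dates. A further amendment states "We have completed data collection 3 times for this group, which consists of our intervention group and our wait-list control group", and adds that by then both arms had been through the seven sessions. The last amendment describes one more assessment, for the wait-list arm only.

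The SAP (Statistical analysis) fits a mixed model to all available observations: up to four per person in the intervention arm (n = 104, 45 clusters) and up to five in the wait-list arm (n = 107, 50 clusters). Time is weeks since baseline. The model tests whether the outcome changes over time and whether that change differs by arm. A time-varying dummy records whether the person had attended sessions by each assessment. The SAP names no contrast at a particular wave, no primary time point and no time-since-treatment variable. It does not say which coefficient answers the primary hypothesis.

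**The concern.** Once the wait-list arm has been treated, an arm comparison no longer sets intervention against usual care. It sets people treated earlier against people treated later. That removes the promised comparator from two of the three hypothesis time points.

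The remaining time point is the only comparison of treated with untreated people that randomisation protects, and the SAP folds it into terms that also draw on the post-crossover waves. If the effect fades, grows or appears late, those terms do not equal the effect at any stated time. A reader of the results could not tell whether that had happened.

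**Working it through.** **Step 1: exposure by wave.** Wave 1 is baseline (October 2017). Waves 2 to 4 are the three later assessments shared by both arms. Wave 5 is wait-list only. Months since the end of the gatherings, intervention / wait-list:

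- Original calendar (gatherings end February and July 2018): March 2018, 1 / untreated; August 2018, 6 / 1; December 2018, 10 / 5.
- Amended calendar: wave 2, about 0 / untreated; wave 3, about 6 / 0 to 3; wave 4, about 12 / 6 to 9. The wait-list figures are ranges because the amended gathering dates are not given.

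Exposure is therefore 0, 1, 1, 1 in the intervention arm and 0, 0, 1, 1 in the wait-list arm. The difference is 0, 1, 0, 0.

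**Step 2: direct arm differences.** Let e(m) be the effect m months after the programme. The expected difference at a wave is e(months, intervention) minus e(months, wait-list), with zero for an untreated arm. A constant effect d gives 0, d, 0, 0. An effect fading 1, 0.5, 0 at 0, 6 and 12 months, with the wait-list arm 0 and 6 months post at waves 3 and 4, gives 0, 1, -0.5, -0.5.

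**Step 3: what the SAP's terms estimate.** The SAP gives no equation. The simplest reading has an intercept, weeks, group, group x weeks and the dummy, with a random intercept. The expected generalised least squares coefficients are

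b = (sum of n X'V⁻¹X)⁻¹ (sum of n X'V⁻¹μ), with V = (1 − ρ)I + ρJ,

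where the sums run over arms with n = 104 and 107, and μ holds the expected outcomes from Step 2. Assessment weeks are 0, 28, 54 and 78, from the amended months. The cluster level, the other covariates and missing data are left out. Everyone is taken to attend as assigned. Effects between the stated months are interpolated linearly.

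| Assumed effect at 0, 6, 12 months | Dummy, wait-list 0 and 6 months post | Dummy, wait-list 3 and 9 months post | Group x time per year (same order) |
|---|---|---|---|
| 1, 1, 1 | 1.00 | 1.00 | 0, 0 |
| 1, 0.9, 0.8 | 1.08 | 1.06 | -0.07, -0.03 |
| 1, 0.5, 0.5 | 1.21 | 1.06 | -0.07, -0.04 |
| 1, 0, 0 | 1.42 | 1.11 | -0.14, -0.09 |
| 0.5, 0.75, 1 | 0.29 | 0.35 | +0.16, +0.07 |
| 0, 0.5, 1 | -0.41 | -0.31 | +0.32, +0.14 |

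The dummy values do not change for within-person correlation ρ from 0.3 to 0.7.

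The group x time column is the SAP's named test. A constant real benefit gives zero there, and a fading one gives a negative slope. Without the dummy, a constant benefit of 1 gives -0.18 per year on the four shared waves.

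**Step 4: sensitivity.** Three other readings were tried: a random slope, categorical wave, and no group x time term. They give 1.1 to 1.45 for 1, 0, 0; 0.26 to 0.44 for the growing pattern; -0.11 to -0.49 for the delayed pattern; and 1.0 for a constant effect. Moving the waves within their stated months and adding the wait-list-only fifth wave at week 92 to 104 (assumed) gives 0.95 to 1.47, 0.21 to 0.37 and -0.58 to -0.25 for the same three patterns.

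The reason is the weighting. The intervention arm's wave-4 mean enters the dummy with weight -0.41 (linear weeks), -0.16 (categorical wave) or -0.53 (no group x time), so a better 12-month result lowers the estimate.

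The time trend matters too. With no effect at all but a one-unit step common to both arms from wave 2 on, linear weeks with five wait-list waves give a dummy of 0.45.

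**Step 5: can wave 2 carry the test?** The baseline-adjusted standard error in SD units is √[(1 − ρ²)(1/104 + 1/107)]. At ρ = 0.5 this is √(0.75 × 0.01896) = 0.119, against 0.100 for the dummy. At ρ = 0.3 and 0.7 the pairs are 0.131 against 0.118, and 0.098 against 0.077. The ratios are 1.11, 1.20 and 1.27 for ρ = 0.3, 0.5 and 0.7. Clustering is ignored in both.

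For detectable differences, assume two-sided 5%, 80% power, mean cluster size 211/95 = 2.22 and design effect 1 + 1.22 × ICC. Unadjusted and with no missing data, the difference is 0.39 SD at ICC 0 and 0.43 SD at ICC 0.20. With ρ = 0.6 these are multiplied by √(1 − 0.36) = 0.8. Allowing 0 to 20% missing data, the adjusted range is 0.31 to 0.39 SD.

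**The case against.** The SAP does not ignore the crossover. Its dummy switches on when each person has attended, and under a constant effect with the right time trend it is unbiased and more precise than a wave-2 contrast. Under mild fading (1, 0.9, 0.8) it is only 2 to 11% above the immediate effect across the readings tried. The larger errors come from sharper patterns, and with the fifth wave included the overstatement for 1, 0, 0 is not universal (0.95 at the low end). All of that stands, so the direction of bias cannot be stated in advance.

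It is also fair that the SAP is a short summary without an equation and calls the dummy a covariate rather than the hypothesis test. This does not help the plan. The test the SAP does name, differing change over weeks, has expectation zero for a lasting benefit when the dummy is in the model.

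The wrong-sign case needs care. In the delayed pattern the immediate effect is zero, so the sign is wrong only against the later effects. A small positive immediate effect can also turn negative: 0.2, 0.6, 1 gives -0.13 with linear weeks and the wait-list arm 0 and 6 months post. With categorical wave it stays just positive, at 0.02.

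Finally, the wait-list session dates under the amended calendar are inferred from the planned sequence and from the statement that both arms had finished after three assessments. The dummy also records attendance rather than assignment, so actual exposure may differ from the 0/1 pattern used here. These points affect the sizes. They do not restore an untreated comparator at waves 3 and 4.

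**Conclusion.** The concern holds and should be corrected. On the documents' own sequence, one of the three promised comparisons has an untreated randomised comparator, and the SAP names no term that isolates it. The other two cannot be made against usual care by any reanalysis of these data.

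That conclusion rests only on the order of treatment and assessment. The dummy coefficients are illustrations. They depend on the assumed effect patterns, on a model equation the SAP does not give, and on assumed wait-list session timing. They show that the dummy equals the effect at all three times when that effect is constant. Otherwise it may sit above the immediate effect, below it, or take the opposite sign.

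**What to change.** Essential:

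1. Limit the randomised effectiveness hypothesis to the first post-intervention wave. Test it with a baseline-adjusted contrast by assigned arm at that wave, keeping the family/clan clusters.
2. Do not interpret the all-wave group-by-time term as a 6- or 12-month effect against usual care. Interpret the dummy only with the constant-effect assumption stated.

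Supporting:

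3. Restate the 6- and 12-month aims as within-participant maintenance, measured from each arm's last assessment before its own sessions (wave 1 for intervention, wave 2 for wait-list). Label them as having no concurrent untreated control. Report the contamination answers alongside, because wave 2 is both the randomised comparison and the wait-list arm's starting point.
4. Report the actual wait-list session dates.

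A time-since-treatment model is an optional sensitivity analysis. With separate effects at each time it can be estimated over the shared waves only if the wait-list arm is about 0 and 6 months post at waves 3 and 4. The standard errors are then 1.6 to 1.7 times (6 months) and 2.1 to 2.5 times (12 months) that of the immediate effect. At 3 and 9 months post it needs a further assumption. With linear interpolation the ratios are 2.4 to 2.65 and 3.6 to 4.1.

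The cost is one added contrast, revised hypothesis wording and a limit on interpretation, with no new data. The late claim becomes weaker, and the wave-2 standard error is about 1.1 to 1.3 times that of the dummy, before clustering and missing data. The SAP is dated 8/23/22, after data collection, so the contrast must be disclosed as post hoc.
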